5.2.7. Electrocardiogram21

5.2.8. Safety Laboratory21

6. INTERIM ANALYSIS22

7. PHARMACOKINETICS22

8. DATA SAFETY AND MONITORING BOARD22

APPENDIX A. CHANGES FROM PROTOCOL..... 1

ABBREVIATIONS:

AE	Adverse Event
BMI	Body Mass Index
CRF	Case Report Form
CSR	Clinical Study Report
CTCAE	Common Terminology Criteria for Adverse Events
DAIDS	Division of AIDS
DSMB	Data and Safety Monitoring Board
IP	Investigational Product
IxRS	Interactive Voice Web Response System
MedDRA	Medical Dictionary for Regulatory Activities
mITT	Modified Intention to Treat
PCR	Polymerase Chain Reaction
PEP	Post-Exposure Prophylaxis
PP	Per Protocol
PROTECT-APT 1	Master Protocol for Early Treatment and Post-Exposure Prophylaxis of COVID-19 Adaptive Platform Trial
PSA	Product-Specific Arm
PT	Preferred Term
SAE	Serious Adverse Event
SAP	Statistical Analysis Plan
SDTM	Study Data Tabulation Model
SOC	System Organ Class
VOC	Variants of Concern
VOI	Variants of Interest
WHO	World Health Organization

REVISION HISTORY

Document Version	Changes Made	Document Date
Version 0.1	Initial draft for review	20JUL2024
Version 0.3	Draft for review	28FEB2025
Version 0.4	Draft for review	07MAY2025
Version 0.5	Draft for review	25JUN2025
Version 0.6	Draft for Review	07JUL2025
Version 0.7	Draft for review	28JUL2025

1. INTRODUCTION

This statistical analysis plan (SAP) expands Section 13 (Statistical Considerations) of the master protocol “Master Protocol for Early Treatment and Post-Exposure Prophylaxis of COVID-19 Adaptive Platform Trial” (PROTECT-APT 1) and Section C 13 (Statistical Considerations) of the Product Specific Appendix (PSA) “Appendix C: A Phase 2 Safety and Efficacy Study of Upamostat for Early Outpatient Treatment of COVID-19”. The final SAP approval by the sponsor will occur before data unblinding. Any changes to the planned analysis will be documented in the Clinical Study Report (CSR).

2. CHANGES FROM THE PROTOCOL

Pharmacokinetic and exploratory objectives will not be analyzed as a part of this SAP. Available data may be included in final Study Data Tabulation Model (SDTM).

3. STUDY OBJECTIVES AND ENDPOINTS

3.1. Primary Objective

To determine if early treatment with upamostat can shorten time to sustained symptom alleviation or resolution in participants infected with SARS-CoV-2.

- **Endpoint:** Time to sustained alleviation of resolution of COVID-19 symptoms. Defined as the number of days from randomization in a PSA to the first day the participant reports all symptoms as mild or none (or returning to pre-illness levels) for at least 3 consecutive days (the first day being considered the Event Day). [Timeframe: Day 0 to Day 28]

3.2. Secondary

- To evaluate the clinical efficacy of Investigational Product (IP) compared to control.
 - **Endpoints**
 - a) Number and proportion of all cause hospitalizations
[Timeframe: Day 0 to Day 28]
 - b) Number and proportion of all cause deaths
[Timeframe: Day 0 to Day 28]
- To determine if early treatment with upamostat can reduce disease severity in participants infected with SARS-CoV-2.
 - **Endpoints**
 - a) Change in overall COVID-19 symptom severity score
[Timeframe: Day 0 to Day 28]
 - b) Number and proportion of participants in each treatment group developing new COVID-19 symptoms graded as severe on the symptom scale
[Timeframe: Day 0 to Day 28]
 - c) Number and proportion of participants who report return to usual state of health

[Timeframe: Days 7, 14, 28, Week 8, Week 12]

d) Number and proportion of participants who report return to usual activities

[Timeframe: Days 7, 14, 28, Week 8, Week 12]

- To determine if early treatment with upamostat can decrease the incidence of hospitalization due to COVID-19.
 - **Endpoint:** Number and proportion of participants hospitalized for COVID-19 [Timeframe: Day 0 to Week 12]
- To evaluate virologic efficacy of upamostat compared to placebo.
 - **Endpoint:** Time to negative PCR [Timeframe: Day 0 to Week 12]

3.3. Exploratory

- To determine the presence and titer of antibodies to SARS-CoV-2 at baseline. The development of antibodies during study participation, and their association with clinical outcome.
 - **Endpoint:** Assay for anti-SARS-CoV-2 IgM and IgG [Timeframe: Baseline and Week 8]
- To assess the impact of host transmembrane protease polymorphism on drug efficacy
 - **Endpoint:** Targeted analysis of polymorphism of known host transmembrane proteases which may be involved in viral entry into host cells.
- Characterize the impact of SARS-CoV-2 genetic variability on primary and secondary outcomes
 - **Endpoints**
 - a) Difference in efficacy outcomes among circulating variants of interest (VOI) and variants of concern (VOC) via geographic and temporal prevalence
 - b) Difference in efficacy outcomes among circulating VOI and VOC via SARS-CoV-2 genome sequencing

3.4. Safety Objectives

To evaluate the safety and tolerability of upamostat compared to control

- **Endpoints**
 - a) Incidence of Serious Adverse Events (SAE)
 - b) Comparison between active and placebo treatment groups in proportion of all and Grade 3 or greater adverse events (as assessed by the National Institutes of Health, Division of AIDS Table for Grading Severity of Adult and Pediatric Adverse Events [DAIDS AE Grading Table], corrected Version 2.1, July 2017)
 - c) Incidence of Adverse Events (AE) causing IP discontinuation
 - d) Incidence of all-cause IP discontinuation or interruption
 - e) Number of participants hospitalized due to adverse events regardless of cause

4. STUDY DESIGN

4.1. Master Protocol

This study is an adaptive, randomized, double blind, platform trial evaluating promising (IP) for safety and efficacy as early outpatient treatment and post-exposure prophylaxis for SARS-CoV-2. This multicenter trial will be conducted in both domestic and international sites. The study will compare IPs to standard of care in non-hospitalized SARS CoV-2 infected participants and uninfected adult contacts of SARS-CoV-2 confirmed cases. The master protocol outlines the core elements of the study.

An independent Data and Safety Monitoring Board (DSMB) will monitor the study both for futility and early efficacy to manage participant risk appropriately.

Safety will be evaluated based on clinical laboratory studies, vital signs, assessment of AE, symptom monitoring and physical exams. Efficacy will be evaluated based on viral testing, symptom scoring and outcome ascertainment.

4.2. Product-Specific Arm

This is a phase 2 adaptive, randomized, double-blind, placebo-controlled platform trial to evaluate the safety and efficacy of upamostat for early outpatient COVID-19 treatment. From the master protocol, following completion of the screening and enrollment requirement, participants who meet the entry criteria for upamostat product-specific arm (PSA), Appendix C, are eligible for randomization to the upamostat Early Treatment arm of the trial.

Probability of randomization to the upamostat PSA arm (Appendix C) will be dependent on the number of PSA enrolling in the Early Treatment indication and the number of PSA arms for which a participant is eligible. For example, if three products are enrolling in the treatment indication at the same time, probability of randomization to the upamostat arm is 1:3. Participants randomized to upamostat PSA arm (Appendix C) will undergo a second blinded randomization to the active agent (upamostat) or placebo. The probability of the second randomization will also be dependent on the number of products enrolling in the indication at that time.

The total sample size was projected to be 300 (150 upamostat, 150 placebo), with safety monitoring planned to allow early stoppage for futility, efficacy, or safety. Details are described in the DSMB Charter.

4.3. Treatment Periods and Dosing

4.4. Sample Size

The maximum planned sample size for the early treatment indication primary analysis was 300 participants with 1:1 allocation to the IP and its control arm. The maximum sample size of 300

participants (150 active and 150 controls) and the adaptive design would provide 90% power to detect a hazard ratio of 1.50 risk (33% reduction in median time to symptom alleviation or resolution) and approximately 80% power for a hazard ratio of 1.42, a 30% reduction in the median time to symptom alleviation or resolution, assuming a median time to symptom resolution of 9 days for the control arm. This assumption is based on review of relevant literature [Menni 2022, Akavian 2022].

4.5. Randomization and blinding (Figure 1)

[figure not shown]
4.5.1. Step 1: Master Protocol and Randomization to PSA

Following completion of the screening informed consent and determination of eligibility under that Master Protocol, participants are stratified as either an eligible SARS-CoV-2 positive case or SARS-CoV-2 negative contact. Once identified as a case or contact, participants then undergo product-specific informed consent, followed by completion of all product-specific screening requirements to determine final eligibility for the available PSA (upamostat).

4.5.2. Step 2: Randomization within PSA

After PSA eligibility determination, participants undergo randomization to the PSA. Following assignment to the upamostat early treatment indication, participants undergo blinded randomization to either upamostat or placebo through the Interactive Voice/Web Response System (IxRS). A shared placebo (control) pool will be considered only if more than one PSA enrolls concurrently.

Figure 1

The randomization statistician prepared an electronic randomization list containing treatment assignments following the randomization sequence uploaded to the Interactive Web Response System (IWRS) operated by the vendor, Clinical One. Details of the specifications are described in the Request for Randomization form. After patient eligibility determination, site staff perform online randomization through Clinical One IWRS. As the study is a double-blind study, neither

patients, nor investigators, nor the Sponsor/CRO study team are aware of treatment assignments prior to the final database lock at the conclusion of the study.

4.6. Blinded Data Review

Prior to scheduled study unblinding, the data may be reviewed in a blinded fashion. Protocol deviations will be reviewed and a determination of the population for per protocol analysis will be made.

4.7. Blinding and Scheduled Study Unblinding

Participants, study staff, and study investigators are not blinded to the first step, randomization to the PSA. Participants are randomized to a PSA for which they meet the eligibility criteria, and which is enrolling in their strata. Randomization to the arm within the respective PSA is implemented through IxRS. Both participants and study investigators will be blinded to the second randomization.

Unblinding will be permitted during the trial in the following events:

- Emergency Unblinding: where knowledge of the treatment randomization is necessary to provide acute medical care or where there is a safety concern by the treating clinician. Details of the unblinding will be captured in the CRF including:
 - Date/timing
 - Reasons for unblinding
 - Name and roles of staff and participants involved in unblinding
 - Required clinical care
 - Event outcome
- To the DSMB for safety monitoring
- Statistical Analysis: unblinded results will be used in the final analyses following final database lock
- Participant notification: All participants will have the option to learn their randomization assignment after their PSA has been completed

In the event unblinding is required every effort will be made to limit this information to those individuals directly involved in the statistical analysis or care decisions and not with study staff.

After the study completes enrollment and patient follow-up, data entry, discrepancy resolution, blinded results reviews, coding and database lock, then the process for full study unblinding will start. Formal request to unblind should come from the Sponsor via a signed “Request to Reveal the Randomization Schedule” FHI 360 form. Once the Sponsor indicates that all requirements for full unblinding have been met, the lead biostatistician will initiate completion and sign-off of this form and document the unblinding process.

4.8. General Issues

General descriptive statistics for numeric variables include

- Continuous variables: mean, standard deviation, percentiles (median, 25th, 75th), minimum, maximum

- Categorical variables: frequency, percentage calculated based on subjects with reported values (i.e., subjects with missing data will not contribute to denominators of percentages)

Descriptive statistics and tabular summaries will be presented by treatment group.

For binary endpoints, proportion of participants with the event will be summarized by treatment group. Comparison between groups will be presented as the difference of proportions with its 95% confidence interval. For categorical endpoints, proportion of participants in each category will be summarized by treatment group

Unless otherwise specified, the following guidelines will be followed when displaying statistics:

- measures of central tendency and percentiles will be displayed with one decimal place more than the raw (collected) data
- measures of variability will be displayed with two decimal places more than the raw (collected) data
- percentages will be displayed with one decimal place
- 1 year = 365.25 days. Number of years is calculated as (days/365.25) rounded up to 1 significant digit.
- 1 month = 30.4375 days. Number of months is calculated as (days/30.4375) rounded up to 1 significant digit.
- For laboratory results collected as < or >, a numeric value, 0.0000000001 will be subtracted or added, respectively, to the value.
- For by-visit observed data analyses, percentages will be calculated based on the number of patients with non-missing data as the denominator.

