Transmembrane serine proteases are essential for viral fusion with the host cell membrane [Yao 2022]. Upamostat is a first-in-class orally administered potent inhibitor of serine proteases targeting multiple indications. Upamostat was initially studied as an inhibitor of urokinase plasminogen activator targeting oncology indications. Subsequent studies revealed that the compound is a potent inhibitor of other serine proteases, especially trypsins. The presumed mechanism is inhibition of spike protein cleavage necessary for viral entry into host cells. It targets human cell rather than viral factors and as such, is expected to be effective against emerging variants. In vitro, upamostat inhibited the original SARS-CoV-2 virus at a concentration well below that achievable in patients. Preliminary results of testing against SARS-CoV-2 BA.5 variant showed a 3-log decrease in viral titer at the highest dose tested. A pilot outpatient study in symptomatic, SARS-CoV-2 positive patients revealed that the drug was well tolerated at both dose levels tested, 200 and 400 mg daily for 14 days [Plasse 2022]. While the study was not powered for efficacy determination, only one of 41 patients (2.4%) receiving upamostat at either of the two doses used developed new severe symptoms on study, versus 4 of 20 (20%) of placebo recipients. Importantly, no upamostat-treated patient was hospitalized for COVID-19 during the study versus 3 of 20 (15%) of placebo recipients. Pharmacologic parameters (reduction in mean D-dimer levels and increased incidence of minor increases in INR and PTT) demonstrated dose-dependent effects.

C 3.3 Study Hypotheses

That early treatment with upamostat among outpatients infected with SARS-CoV-2 can shorten time to sustained symptom alleviation or resolution as compared to standard treatment.

C 3.4 Risk/Benefit Assessment

C 3.4.1 Known Potential Risks

C.3.4.1.1 Risks Associated with Upamostat

To date, 230 subjects have been treated with upamostat in clinical trials, including 41 in a recently concluded pilot study of upamostat for outpatient treatment of COVID-19.

In randomized clinical trials the only events attributable to upamostat were transient increases in transaminases, rash and, in patients receiving capecitabine, palmar-plantar erythrodysesthesia syndrome.

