4.10. Derivations, Data Handling Conventions and Missing Data

Baseline will be defined as the last assessment prior to the first dose date/time (or randomization if patient was not treated).

Study Day will be derived as (assessment date – date of first dose) + 1.

Event durations in days will be derived as (end date – start date) + 1.

Missing data will not be imputed unless otherwise specified elsewhere in this SAP. Missing dates or partially missing dates will be imputed conservatively for adverse events and concomitant medications. Specific rules for the handling of missing or partially missing dates for adverse events and concomitant medications are provided in Appendix A A.

By-visit endpoints will be analyzed using observed data unless otherwise specified. For observed data analyses, missing data will not be imputed, and only the observed records will be included.

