5.2.2. Secondary Outcomes: Clinical

- Number and proportion of all cause hospitalizations
 - Timeframe: Day 0 to Day 28
- Number and proportion of all cause deaths
 - Timeframe: Day 0 to Day 28
- Change in overall COVID-19 symptom severity score
 - Timeframe: Day 0 to Day 28
 - A mixed model repeated measure model will be used to model the symptom severity score (Overall Symptom Severity) at each day using the baseline symptom score, participant, day, and treatment by day as covariates. The treatment effect by day will be summarized.
- Number and proportion of participants in each treatment group developing new COVID-19 symptoms rated as severe
 - Timeframe: Day 0 to Day 28
 - A Cox proportional hazards model will be used to analyze development of new severe symptoms. A new severe symptom is defined as scoring from 0 to 1 on any symptom in the questionnaire and subsequently scoring a 3 for that symptom (or a 2 for change in taste or smell). Treatment arm will be modeled with a proportional hazard effect. The hazard ration will be summarized.
- Proportion of participants who report a return to usual state of health
 - Timeframe: Day 7, Day 14, Day 28, Week 8, Week 12
 - A Cox proportional hazards model will be used to analyze the rime to return to usual state of health. Participants without symptomatic COVID-19 will be considered a 0 for return to usual health. Treatment arm will be modeled with a proportional hazard effect. The hazard ration will be summarized.
 - A Kaplan-Meier curve of time to return to usual state of health will be presented.
- Proportion of participants who report a return to usual activities
 - Timeframe: Day 7, Day 14, Day 28, Week 8, Week 12
 - A Cox proportional hazards model will be used to analyze the time to return to usual activities. Participants without symptomatic COVID-19 will be considered a 0 for return to usual activities. Treatment arm will be modeled with a proportional hazard effect. The hazard ratio will be summarized.
 - A Kaplan-Meier curve of time to return to usual activities will be presented.

Analysis population: The mITT population will be used for secondary endpoint analyses. Change in overall COVID-19 symptom severity score will be repeated with the Per Protocol Population and the Baseline COVID-19 PCR Positive Population.

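### By-visit percentages for return to usual health and activities drop participants who have died, or are in hospital for COVID-19 and give no answer, although they are known not to have returned

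*SAP*

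**What the plan says.** SAP 3.2 lists the first endpoint as "Number and proportion of participants who report return to usual state of health" and words return to usual activities in parallel. SAP 5.2.2 gives the time points for both: "Timeframe: Day 7, Day 14, Day 28, Week 8, Week 12". It names mITT as the population for secondary endpoints.

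The denominator comes from the general sections:

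- SAP 4.8, categorical variables: "subjects with missing data will not contribute to denominators of percentages".
- SAP 4.8, by-visit analyses: "For by-visit observed data analyses, percentages will be calculated based on the number of patients with non-missing data as the denominator".
- SAP 4.10: "By-visit endpoints will be analyzed using observed data unless otherwise specified", and for such analyses "missing data will not be imputed, and only the observed records will be included".

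SAP 4.8 carries the result into the treatment comparison for binary endpoints: "Comparison between groups will be presented as the difference of proportions with its 95% confidence interval".

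Special missing-data rules exist only for the primary endpoint (4.10.1) and time to negative PCR (4.10.2). For the two return endpoints, 5.2.2 has one value rule, for participants without symptomatic COVID-19. It is silent on death, hospitalisation and non-response, and so is protocol C 13.5.1.2. SAP 5.2.2 also plans a Cox model and a Kaplan-Meier curve for each endpoint, with no rule for death or censoring.

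**The concern.** For most missed visits the answer really is unknown. In two situations it is not. A participant who has died has not returned to usual health or activities, and neither has one who is in hospital for COVID-19 on the visit date. Treating these as missing discards a known unfavourable outcome and turns an mITT comparison into one among responders.

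If such outcomes are unevenly spread between arms, the arm with more of them loses its worst participants from the denominator and looks better than it should. The recovery difference could then understate a benefit or understate a harm.

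**Working it through.** The plan states no figure for non-response, death or return to health, so there is nothing to reproduce. The check follows the rule through and then sizes its effect under stated assumptions.

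**Step 1: does any exception apply?** SAP 4.10 allows exceptions where specified. Sections 4.10.1, 4.10.2 and 5.2.2 contain none for these endpoints, so the observed-data rule governs.

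**Step 2: formula.** In each arm let p be the return rate among responders, and h the share of mITT participants who are dead, or in hospital for COVID-19 and silent, at the visit. Leave other missed visits aside. Subscript 1 is upamostat, 0 is placebo.

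- SAP rule: difference = p1 − p0.
- Counting these participants as not returned: difference = p1(1 − h1) − p0(1 − h0).
- Shift = p0·h0 − p1·h1. With p1 = p0 = p this is p × (h0 − h1).

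**Step 3: numbers.** Both p and the gap in h are assumptions.

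| Gap h0 − h1 | Shift at p = 60% | Shift at p = 80% |
|---|---|---|
| 1% | 0.60 × 1 = 0.6 points | 0.80 × 1 = 0.8 points |
| 2% | 1.2 | 1.6 |
| 5% | 3.0 | 4.0 |

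The sign reverses if the excess is on upamostat. If h is equal in both arms and p is too, the shift is zero and only the two percentages fall.

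**Step 4: as head counts.** Take the planned 150 per arm, 60% return among responders in both arms, and 3 such participants on placebo and none on upamostat. Placebo has 147 responders and an expected 0.60 × 147 = 88.2 returns. The SAP rule gives 88.2/147 = 60.0% and a difference of 0. The full denominator gives 88.2/150 = 58.8% and a difference of +1.2 points.

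**Step 5: set against precision.** In that example the Wald 95% interval under the SAP rule is about ±11.1 points. At an assumed 75 per arm, with 1 such participant on placebo, it is about ±15.7. The smaller size is relevant because SAP Appendix A says enrolment ended before the interim trigger. A shift of 0.6 to 3 points is well inside either interval.

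**The case against.** The strongest reply is that these participants do not vanish from the results.

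- The Cox and Kaplan-Meier analyses keep a participant who has not returned in the risk set until censoring.
- Deaths and all-cause hospitalisations to Day 28, and COVID-19 hospitalisations to Week 12, are separate secondary endpoints.
- Protocol C 12.1 keeps hospitalised participants in the study with other activities continuing, and remote visits may be by phone or video. Anyone who answers that they have not returned is already counted correctly.

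All of this stands and limits the point to the by-visit proportions and their differences. It does not remove it. No rule keeps a participant who died as not recovered, so ordinary censoring at death would treat that person as someone who might still have recovered. The death endpoint also stops at Day 28, while the return endpoints run to Week 12.

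A reader might infer a much larger effect from the pilot, in which "no upamostat-treated patient was hospitalized for COVID-19 during the study versus 3 of 20 (15%) of placebo recipients". Putting 15% into the formula at 60% return gives 0.15 × 0.60 = 9 points. The documents do not support that. The 15% is cumulative incidence over the whole pilot and rests on three events. Using it for h requires every participant ever admitted to be in hospital on the same visit day and none to answer. If, purely as an assumption, half were in hospital that day and half of those were silent, h would be 0.15 × 0.5 × 0.5 = 3.75% and the shift 0.0375 × 0.60 = 2.25 points.

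A reader might also infer that the rule must pull the result toward no effect. That too is unsupported, because the documents give no non-response rates or reasons by arm.

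**Conclusion.** The point holds as a modest defect in two secondary endpoints. As written, the SAP removes participants whose unfavourable status is known, and the reduced denominator feeds a between-arm difference with a confidence interval. The likely size is small: 0.6 to 3 points for gaps of 1% to 5%, assuming 60% return among responders in both arms. The direction cannot be predicted. It would be zero if both the non-reporting and the return rates among responders were equal between arms.

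It does not affect the primary endpoint, and it does not mean that deaths or admissions go unreported. The case for changing it is that the correction is cheap and replaces an accidental convention with a defensible definition.

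**What to change.** Add to SAP 5.2.2, for both return endpoints:

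> In the by-visit proportions, a participant who has died by the visit, or who is in hospital for COVID-19 on the visit date and gives no answer, remains in the mITT denominator and counts as not returned. In the Cox and Kaplan-Meier analyses, a participant who dies without having returned is kept event-free to Week 12 and is not censored at death. Percentages based on observed data only are reported as a sensitivity analysis.

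Insert a cross-reference to this exception in the observed-data rules of 4.8 and 4.10. The handling of other missed visits can be left to the sponsor, since their status is unknown and more than one method is reasonable.

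The cost is a few sentences, an entry in SAP Appendix A and slightly lower recovery percentages. Deaths and COVID-19 hospitalisations are already collected for other endpoints, and the protocol has COVID-19 hospitalisations adjudicated before unblinding. The rule does need admission and discharge dates, which are assumed to be available because the case report form is not in the documents. The change is most credible before unblinding. If made later, record it with its timing in the Clinical Study Report.
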